 A comprehensive skin evaluation will be performed by the Investigator or qualified designee. The skin exam should include a full body skin exam (head-to-toe skin examination). Any concerning lesions identified during the Screening Period will be biopsied and results known to be benign prior to the first dose of setmelanotide. If the pre-treatment biopsy results are of concern, the patient will be excluded from the trial. Additionally, any new lesion or change in an existing lesion identified during the course of the trial must be evaluated by a dermatologist and biopsied, if clinically indicated in the opinion of the dermatologist.

 Weight (kg) is to be measured at the clinic using the same scale throughout the trial or at home (during virtual visits or visiting nurse visits) using the same scale provided to the patient as part of the clinical trial. Weight should be measured after patients have attempted to empty their bladders and after fasting for

at least 8 hours. Patients are to wear light clothing or underwear and no shoes, with empty pockets, and will be weighed at approximately the same time of day. All measurements will be recorded to the nearest tenth kg if reported with a digital scale, or half kg with a mechanical scale.

7 Height (cm) will be measured, without shoes, socks or hats, using a wall-mounted stadiometer. The stadiometer should be calibrated by site personnel on a daily basis prior to height assessment. All measurements will be done in triplicate at each time point and recorded to the nearest half cm.

8 [REDACTED]

9 All blood pressure (BP) and heart rate (HR) measurements are to be obtained in a sitting position following at least 5 minutes of rest. All measurements will be taken in triplicate, approximately 2 minutes apart. When possible, BP should be taken in the non-dominant arm using the same methodology (automated or manual) throughout the trial.

10 A single 12-lead ECG will be performed. If an ECG is not practical in a young patient, it may be replaced by a rhythm strip and HR and PR interval should be documented.

11 A daily question querying whether the patient completed their daily injection will be asked via electronic diary. Paper versions can be used, if required.

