### **8.2. Efficacy Assessments**

#### **8.2.1. Weight and Height**

Weight (kg) and height (cm) will be recorded at the time points designated in the SoA ([Table 1](#)). All measurements will be done in triplicate at each time point.

Weight should be measured after patients have attempted to empty their bladders and after fasting for at least 8 hours. Patients are to wear light clothing or underwear and no shoes, with empty pockets, and will be weighed at approximately the same time of day. All measurements will be recorded to the nearest 10th of a decimal place if reported with a digital scale, or half kg with a mechanical scale.

Whenever possible, the same scale should be used throughout the trial, including the Screening visit, and should be calibrated on a regular basis per manufacturer's specifications.

Patient's weight will be monitored closely during the trial. If a patient's weight decreases to below 15 kg, the Investigator and Sponsor will discuss the patient's status and will jointly determine if that patient should continue the current dose, decrease the dose or discontinue treatment with setmelanotide temporarily or permanently. A dose reduction to 0.25 mg QD can be considered in such scenarios or in case of tolerability concerns. These dose adjustments are considered adequate to help attain and maintain appropriate body weight in growing pediatric patients

Height (cm) will be measured without shoes, socks, or hats, using a wall-mounted stadiometer. The stadiometer should be calibrated by site personnel on a daily basis prior to height assessment. All measurements will be done in triplicate at each time point and recorded to the nearest half centimeter. Both weight and height measurements will be used to determine BMI and BMI-related assessments (i.e., Z-score and percentiles).

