### 9.1 Primary Efficacy Endpoints

#### 9.1.1 Proportion of Patients with a Decrease from Baseline to 52 Weeks in BMI Z-score $\geq 0.2$

A “responder” is defined as a decrease from baseline to 52 weeks in the patient’s BMI z-score of  $\geq 0.2$ . The WHO Child Growth Standards 2007 will be used for BMI z-score. At each visit, an indicator variable will be created to identify patients that have a decrease in BMI z-score from baseline of 0.2 or more, allowing for the analysis of proportion of patients who meet the “responder” definition. The proportion and the corresponding 2-sided 95% CI using the Clopper-Pearson method will be reported for each visit. Sample SAS code to calculate the BMI z-score can be found at <https://www.who.int/tools/child-growth-standards/software>.

#### 9.1.2 Mean Percent Change in BMI from Baseline to Week 52

For the analysis of Mean percent change in BMI from baseline, percent changes in BMI from baseline over time will be summarized using descriptive statistics. Mean percent change in BMI from baseline over time will also be provided graphically. A 2-sided 95% CI with Student’s *t*-distribution will be provided for Mean percent change in BMI from baseline. In addition, patient figures showing the percent change in BMI from baseline will be created. Information on the patient’s baseline BMI will be included in the figure.

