1. A complete physical examination will be conducted at screening and at the End of Treatment (EOT) Visit. At other timepoints, an abbreviated examination will be performed. The abbreviated examination should focus on heart, lungs, skin, neurologic exam, and any areas of previous abnormal findings, noting any changes from baseline. Tanner staging should be performed at Screening and at the EOT (Week 52) visit. It may be done at additional visits, at the discretion of the Investigator.
2. A comprehensive skin evaluation will be performed by the Investigator or qualified designee. The skin exam should include a full body skin exam (head-to-toe skinexamination). Any concerning lesions identified during the Screening Period will be biopsied and results known to be benign prior to first dose of setmelanotide. If the pre-treatment biopsy results are of concern, the patient will be excluded from the study. Additionally, any new lesion or change in an existing lesion identified during the course of the study must be evaluated by a dermatologist and biopsied, if clinically indicated in the opinion of the dermatologist.
3. Weight (kg) is to be measured at the clinic using the same scale throughout the study or at home (during virtual visits or visiting nurse visits) using the same scale provided to the patient as part of the clinical study. Weight should be measured after patients have attempted to empty their bladders and after fasting for at least 8 hours. Patients are to wear light clothing or underwear and no shoes, with empty pockets, and will be weighed at approximately the same time of day. All measurements will be recorded to the nearest tenth kg if reported with a digital scale, or half Kg with a mechanical scale.
4. Height (cm) will be measured, without shoes, socks or hats, using a wall-mounted stadiometer. The stadiometer should be calibrated by site personnel on a daily basis prior to height assessment. All measurements will be done in triplicate at each time point and recorded to the nearest half cm.
- 5.
6. All blood pressure (BP) and heart rate (HR) measurements are to be obtained in a sitting position following at least 5 minutes of rest. All measurements will be taken in triplicate, approximately 2 minutes apart. When possible, BP should be taken in the non-dominant arm using the same methodology (automated or manual) throughout the study.

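### Mechanical-scale weights may be recorded to the nearest 0.5 kg even at Baseline and Week 52, so where such a scale is used, rounding can flip responder status for children close to the 0.2 BMI z-score cut.

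*Protocol*

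**What the plan says.** Protocol Table 1, footnote 6, sets the recording precision for weight: "All measurements will be recorded to the nearest tenth kg if reported with a digital scale, or half kg with a mechanical scale". Protocol 8.2.1 again allows recording to a tenth with a digital scale "or half kg with a mechanical scale", and SAP 16.1 footnote 3 has the same rule: "All measurements will be recorded to the nearest tenth kg if reported with a digital scale, or half Kg with a mechanical scale". The rule covers every visit at which weight is taken. Neither document requires a digital scale at any visit.

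Footnote 6 asks for one scale throughout, whereas 8.2.1 asks for this only where possible. Neither names the type of scale. On replicates, 8.2.1 says: "All measurements will be done in triplicate at each time point". SAP 3.5.1 and 9 average the replicate values before BMI is calculated. Height is also taken in triplicate and is recorded to the nearest half centimetre (Table 1 footnote 7; 8.2.1).

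The first primary endpoint (SAP 9.1.1) flags "patients that have a decrease in BMI z-score from baseline of 0.2 or more" and reports the proportion with a Clopper-Pearson interval. On the reference, SAP 9.1.1 says: "The WHO Child Growth Standards 2007 will be used for BMI z-score". The second primary endpoint is mean percent change in BMI (SAP 9.1.2). Entry weight may be as low as 15 kg, and about 10-15 children are planned.

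**The concern.** A yes/no endpoint with a fixed cut needs measurement error that is small relative to the cut. Here the coarser permitted weight step may be about as large as the weight change that the cut represents. A child whose BMI z-score truly fell by somewhat more or less than 0.2 could then be counted on the wrong side because of how two weights were rounded.

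No hypothesis test is planned, so the responder count and its interval are themselves the first primary result. With 10-15 children, one wrong label moves the rate by 1/15 = 6.7 to 1/10 = 10 percentage points. For example, 8/10 (95% CI 44% to 97%) becomes 7/10 (35% to 93%). The interval makes no allowance for misclassification. The additional efficacy analysis in SAP 9 (LOCF) concerns missing values, not measurement error.

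**Working it through.** The plan states no measurement-error figure, so there is nothing to reproduce.

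**Inputs from the documents.** Weight step 0.5 kg or 0.1 kg; height step 0.5 cm; cut 0.2 z; minimum weight 15 kg; three readings averaged.

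**Assumptions.** S, the BMI in kg/m² per z-unit in the obese range, is 1.5-2.5. Height h is 0.90-1.15 m. The documents give neither.

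**1. The cut in kilograms.** At a given height, 0.2 z corresponds to t = 0.2 × S × h². The 0.5 kg step is 0.5/0.661 = 0.76 to 0.5/0.243 = 2.1 times t. With S = 1.2-3.0 and h = 0.85-1.20 m, t widens to 0.17-0.86 kg.

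**2. Rounding error in the change.** Each weight is off by up to 0.25 kg. Taking the two errors as independent and uniform, their difference is triangular on ±0.5 kg, and the chance that it reaches d in one direction is (0.5 - d)²/0.5 for d below 0.5, and 0 otherwise. A child with no true change needs d = t to be called a responder. At -0.1 z the child needs d = t/2, and by symmetry a child at -0.3 z is missed with the same chance.

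| S | h (m) | t (kg) | False response, no change | Wrong label at -0.1 or -0.3 z |
|---|---|---|---|---|
| 1.5 | 0.90 | 0.243 | 0.257²/0.5 = 13% | 0.3785²/0.5 = 29% |
| 2.0 | 1.00 | 0.400 | 0.100²/0.5 = 2% | 0.300²/0.5 = 18% |
| 2.5 | 1.15 | 0.661 | 0 | 0.169²/0.5 = 6% |

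At -0.6 z the error must reach 0.4 z. Even in the first row this is 0.486 kg, with chance 0.014²/0.5 = 0.04%. In simulation it was 0.5% or less.

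**3. Growth.** Height is not fixed over a year. Simulating 7 cm of growth (S = 2.0, starting height 1.00 m, identical replicate readings, 0.5 kg recording) gives wrong labels of 17% at -0.10 z, 33% at -0.15 z, 29% at -0.25 z and 14% at -0.30 z. The result does not depend on holding height fixed.

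**4. Triplicates.** If all three readings round to the same half kilogram, averaging changes nothing. If readings vary with an assumed SD of 0.1 kg, averaging lowers the wrong-label rate from 17% to 9% at -0.10 z and from 33% to 26% at -0.15 z. With 0.1 kg recording and the same reading noise, the rates are 0.6% and 10%.

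**5. What 0.1 kg recording leaves.** Weight rounding then contributes at most 0.1 kg to the change, which is less than the smallest 0.1 z distance (0.1 × 1.5 × 0.90² = 0.12 kg). Height rounding remains: up to 0.25 cm per visit, or 2 × BMI × 0.0025/h, about 0.08 kg/m² (BMI 18, 1.10 m) to 0.14 kg/m² (BMI 26, 0.95 m). Simulating both (0.1 kg weights, half-centimetre heights, assumed baseline BMI 19-25, 5-9 cm growth, identical replicates) leaves wrong labels of about 0-9% at -0.1 z and 8-25% at -0.15 z. At S = 2.0 and 1.00 m the figures are 1.4% and 16%.

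**6. Second primary endpoint.** A 0.5 kg step is 0.5/15 = 3.3% of BMI at 15 kg and 0.5/30 = 1.7% at 30 kg. The rounding SD of the change is √2 × 0.5/√12 = 0.204 kg, or 1.36% of 15 kg. If every child weighed 15 kg on a mechanical scale, this would add an SE to the mean of 1.36/√15 = 0.35 to 1.36/√10 = 0.43 percentage points.

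**The case against.** The half-kilogram rule applies only to mechanical scales, and the documents do not show that any of the 5-8 planned centres uses one. If all weigh digitally, the effect is nil. This stands: the point concerns what the plan permits, not what is known to have happened.

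The comparison with the cut rests on assumed z-unit sizes and heights. This also stands, which is why ranges are given.

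Only children near the cut are exposed. The documents give no expected distribution of z-score change, and protocol 3.3 describes robust weight reduction in the programme, so few children may lie there. This stands too. Rounding is symmetric, and no systematic bias in either primary endpoint has been shown.

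The same-scale rule exists already, and much of the remedy may come late. Protocol version 5.0 is dated June 2023, the synopsis estimates last completion in September 2023, and SAP 12 sets an interim for 23 August 2023. Many Baseline weights have therefore probably been taken. Requiring a digital Week 52 weight from a child weighed mechanically at Baseline would break the same-scale rule and add a between-scale difference. The fix has to allow for that.

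None of this supplies a reason to keep the coarse option at the two visits that define the primary endpoints.

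**Conclusion.** The point holds in a conditional form. The plan expressly permits 0.5 kg recording at Baseline and Week 52. Under the stated assumptions that step is comparable to the weight equivalent of a 0.2 z fall. Where a mechanical scale is used, rounding mislabels about 6-29% of children truly at -0.1 or -0.3 z and 0-13% of those with no change, but essentially none at -0.6 z. Triplicate averaging reduces this only partly. The added noise in mean percent change in BMI is small.

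A reader might infer that rounding makes the responder rate as a whole unreliable or inflates it. The documents do not support that: scale use is unknown, the error is symmetric, and only children near the cut are affected. A reader might also infer that recording to 0.1 kg would end misclassification. It would not, because half-centimetre heights leave some. The point is worth correcting but does not undermine the trial.

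**What to change.** In Table 1 footnote 6, protocol 8.2.1 and SAP 16.1 footnote 3, for weights still to be taken at Baseline and at Week 52 or early termination:

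- require a calibrated digital scale recorded to 0.1 kg, the same scale for each child;
- delete the half-kilogram option for those visits;
- align 8.2.1 with footnote 6 on the same-scale rule and on the wording of digital precision.

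For a child whose Baseline weight was already taken on a mechanical scale:

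- keep that scale at Week 52, adding a digital reading if one is available;
- record the scale type and flag the child in the listing.

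In SAP 9.1.1, add a sensitivity analysis that repeats the responder count and its interval without the flagged children. With so few patients it would be read alongside the main count, not in place of it.

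The cost is a digital scale at any site lacking one and one extra sensitivity table. Scale type must be available for the flag; the case report form is not among the documents, so whether it is already collected cannot be told. No visits or procedures are added beyond an optional second weighing for flagged children.

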## 6. SELECTION AND WITHDRAWAL OF PATIENTS

### 6.1. Inclusion Criteria

1. Patients must have obesity due to either:
  - a. POMC, PCSK1, or LEPR deficiency, confirmed by genetic testing demonstrating biallelic variants that are interpreted as pathogenic, likely pathogenic, or of undetermined significance (VUS) by the American College of Medical Genetics and Genomics criteria (ACMG), **or**
  - b. BBS as defined by both (1) the Beales Criteria, 1999 ([Beales 1999](#), [[Appendix 1](#)]) AND (2) genetic confirmation of homozygous or compound heterozygous loss-of-function mutation in BBS genes.
2. Age between 2 to <6 years at the time of informed consent.
3. Obesity, defined as BMI  $\geq$ 97th percentile for age and gender AND body weight of at least 15 kg at the time of enrollment.
4. Symptoms or behaviors of hyperphagia at any time during the patient's life, as determined by the Investigator at screening.
5. Parent or guardian of patient is able to communicate well with the Investigator, to understand and comply with the requirements of the trial (including the once daily [QD] injection regimen and all other trial procedures) and is able to understand and sign the written consent.

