## 9 Efficacy Analysis

Efficacy analyses of weight, waist circumference, BMI, and BMI z-scores will be conducted using the data as observed (DAO) with no imputation for missing data. Additional analyses will be conducted using the last observation carried forward (LOCF) to impute any missing data.

If needed, weight and height will first be converted into kilograms and meters, respectively. Given that height and body weight are collected in triplicates at each visit, these will first be aggregated into one averaged value per visit. Visits will then be compared against the analysis visit window (described in [Section 4.2](#)) to select the appropriate averaged values prior to calculating weight, BMI, BMI z-score, and changes. If height is missing for an analysis visit, then height will be imputed using LOCF.

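### Recording height only to the nearest 0.5 cm adds avoidable noise to the 0.2 z-score responder call, which matters for children whose true fall lies close to the cut

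*Protocol*

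**What the plan says.** Protocol Table 1, footnote 7, specifies a wall-mounted stadiometer, calibrated every day, and continues: "All measurements will be done in triplicate at each time point and recorded to the nearest half cm". Protocol section 8.2.1 gives the same rule: "All measurements will be done in triplicate at each time point and recorded to the nearest half centimeter". SAP section 16.1, footnote 4, repeats it. Digital weights, by contrast, are kept to 0.1 kg; mechanical scales may be read to 0.5 kg.

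Height then drives the efficacy results. Protocol section 8.2.1: "Both weight and height measurements will be used to determine BMI and BMI-related assessments". SAP section 9: "Given that height and body weight are collected in triplicates at each visit, these will first be aggregated into one averaged value per visit". For the first primary endpoint, SAP section 9.1.1 says that "an indicator variable will be created to identify patients that have a decrease in BMI z-score from baseline of 0.2 or more", and on the reference: "The WHO Child Growth Standards 2007 will be used for BMI z-score". The second primary endpoint, mean percent change in BMI, uses the same heights.

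Neither document gives a reason for 0.5 cm, an estimate of reading error, an expected height or BMI distribution, or the BMI units that make up one z-unit. About 10-15 children are planned, with descriptive analysis and no hypothesis test.

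**The concern.** The plan pays for a precise height (daily calibration, three readings) and then discards part of that precision when the value is written down. Because height is squared, a relative error in height becomes about twice that in BMI. Errors at Baseline and at Week 52 both enter the change.

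Averaging three readings removes rounding error only if the readings fall in different half-centimetre steps. If careful repeat readings all round to the same value, the mean carries the full rounding error. So the rule takes most from the sites that measure best.

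The responder call is a yes/no cut at a fall of 0.2 z. With 10-15 children, one child changing sides moves the response rate by 1/15 = 7 to 1/10 = 10 percentage points.

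**Working it through.** The plan states no measurement-error figure, so there is none to reproduce.

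**Inputs from the documents.** Recording step 0.5 cm; three readings averaged; responder cut 0.2 z; entry criteria "Age between 2 to <6 years at the time of informed consent" and "body weight of at least 15 kg at the time of enrollment".

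**Assumptions, not in the documents.** Height 90-115 cm at Baseline, growth 4-8 cm over the year, BMI 22-28 kg/m2, U = 1.5-2.5 kg/m2 per z-unit. Illustrative child: height 100 cm, BMI 25, U = 1.7.

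**1. Typical size if the three readings agree.** Rounding SD per visit = 0.5/√12 = 0.144 cm. SD of the BMI change ≈ BMI × 2 × 0.144 × √2 / height. For the illustrative child this is 25 × 2 × 0.144 × 1.414 / 100 = 0.102 kg/m2, and 0.102/1.7 = 0.060 z (30% of 0.2). Simulating 400,000 children over the assumed ranges gives 0.097 kg/m2. Dividing by 2.5 and by 1.5 gives about 0.04-0.065 z, or 20-32% of the threshold.

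**2. Effect of averaging (illustrative child).**

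| Within-session reading SD (cm) | All three readings round alike | SD from rounding (z) | Share of 0.2 z |
|---|---|---|---|
| 0 | 100% | 0.060 | 30% |
| 0.05 | 83% | 0.048 | 24% |
| 0.1 | 66% | 0.039 | 19% |
| 0.15 | 50% | 0.035 | 18% |
| 0.3 | 21% | 0.035 | 17% |

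**3. Worst case.** Opposite errors of 0.25 cm at the two visits: 25 × [(100/99.75)² − (100/100.25)²] / 1.7 = 0.147 z (74% of 0.2). At 90 cm it is 0.163 z (82%). Over wider assumptions (height 85-120 cm, BMI 20-35, U 1.5-2.5) the worst case runs from 33% to 137% of the threshold. It is rare: for the illustrative child, an error above 0.14 z has probability of about 0.2%, even with no benefit from averaging.

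**4. Who is exposed (illustrative child, readings agree).** The probability of being counted a responder is:

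| True fall (z) | ≤0.05 | 0.10 | 0.15 | 0.20 | 0.25 | 0.30 | ≥0.40 |
|---|---|---|---|---|---|---|---|
| P(responder) | 0.00 | 0.05 | 0.22 | 0.50 | 0.78 | 0.95 | 1.00 |

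**5. A child with a true fall of 0.25 z: share missed.** Simulation over the assumed ranges, reading error included:

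| Reading SD (cm) | U | 0.5 cm recording | 0.1 cm recording | Difference (points) |
|---|---|---|---|---|
| 0 | 1.5 | 23% | 0% | 23 |
| 0 | 2.5 | 11% | 0% | 11 |
| 0.1 | 1.5 | 15.6% | 3.2% | 12.4 |
| 0.1 | 2.5 | 4.5% | 0.1% | 4.4 |
| 0.3 | 1.5 | 27.9% | 25.8% | 2.1 |
| 0.3 | 2.5 | 16.4% | 14.0% | 2.4 |

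Misses with 0.1 cm recording are within about half a point of those with no rounding at all. The last column is therefore essentially what the half-centimetre rule adds to reading error.

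**6. Mean percent change in BMI.** Rounding errors run both ways, and their average in the simulation is essentially zero.

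**7. After the change.** With 0.1 cm at both visits and agreeing readings, the SD falls from about 0.097 to 0.019 kg/m2. If only Week 52 is recorded to 0.1 cm, it falls to about 0.072 kg/m2.

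**The case against.** **A reader might infer that rounding noise is close to the size of the threshold.** Errors of about 80% of 0.2 z are attainable, but they need nearly maximal and opposite rounding at the two visits. The figure also depends on heights, BMI values and a z-scale that the documents do not give. It is neither typical nor a ceiling. The SAP's averaging reduces the noise further once readings differ.

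**A reader might infer that the response rate is distorted.** The 0.25 z child sits deliberately near the cut. With true falls spread out (assumed mean/SD of 0.5/0.5 or 1/1 z), total misclassification is about 1-5%, reading error included. The net shift in the response rate is at most 0.3 percentage points, because errors run both ways. This limits the consequence to individual borderline children, and the planned Clopper-Pearson interval is far wider than that shift.

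**A reader might infer that 0.1 cm recording abolishes misclassification.** It does so only when repeat readings agree almost exactly. At reading SD 0.3 cm, reading error dominates and little is gained.

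**A reader might infer that growth safety is compromised.** Protocol Table 1, footnote 18, names bone age for growth-related safety concerns. A rounding SD of 0.144 cm is also small against the assumed 4-8 cm of yearly growth.

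**Timing.** Protocol version 5.0 is dated 22 June 2023, the synopsis estimates last completion in September 2023, and the SAP plans its interim analysis for 23 August 2023. On that schedule all Baseline heights had been taken before this version, and few Week 52 heights remained. This objection stands and reduces the gain.

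**Other sources.** A mechanical scale read to 0.5 kg can err by more: at worst 1.7-3.3% of BMI at 30-15 kg, against about 1% from height. That is true where such scales are used. The height rule, however, applies to every child at every visit.

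**Conclusion.** The point holds as a modest, avoidable loss of precision. Under the assumed height, BMI and z-scale, half-centimetre recording contributes an SD of about 20-32% of the responder threshold if repeat readings agree, and less if they vary. It can change the call only for children whose true fall is roughly 0.1-0.3 z. For a true fall of 0.25 z, the cost is 11-23 percentage points of missed responders with agreeing readings, and about 2-12 points at reading SD 0.1-0.3 cm. The documents do not support a claim of bias in either primary endpoint. How many children lie near the cut cannot be told from them. The case for acting is that the loss has no stated reason and is cheap to reduce.

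**What to change.** In Protocol Table 1 footnote 7, Protocol section 8.2.1 and SAP section 16.1 footnote 4, require each of the three height readings to be recorded to the nearest 0.1 cm. For visits already completed, use the finer source reading where a site wrote one down.

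The cost is a short amendment to two documents; no visit, procedure or burden on the child is added. The drawback is mixed precision within a child whose Baseline stays at 0.5 cm, for whom only the partial gain in step 7 is available. Sites may not hold finer readings, since the protocol did not ask for them. If no Week 52 visits remain, recovery from source is the only part that can still help this trial, and the wording change is for later protocols.
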